7.3.2 Structural features

In the human genome, the HGF gene consists of 18 exons and 17 introns, and two isoforms are expressed through alternative splicing between exon 4 and exon 5. (A)

HGF-X genes are genomic-cDNA hybrid genes in which intron 4 sequences of various lengths are inserted between exon 4 and exon 5 of the HGF cDNA. (B)

HGF-X7 is the most optimized gene among the HGF-X genes in terms of gene expression efficiency, and it effectively expresses both HGF isoforms. (C)

[REDACTED]

[REDACTED]

[REDACTED]

[REDACTED]

(2) C

Eq
sk
V
H

8. Study objective and hypothesis

8.1 Objective

The purpose is to evaluate the following two aspects of the treatment method involving direct myocardial injection of VM202RY into reversible coronary artery regions where complete reperfusion cannot be achieved by coronary artery bypass surgery.

(a) Safety

(b) Preliminary efficacy

: Determination of the optimal dosage through dose escalation and verification of therapeutic effects

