COVER PAGE

Clinical Protocol and Statistical Analysis

NCT Number: NCT01422772

Official Title:

Open-label, non-comparative, dose-escalation, single-center, phase 1 trial to evaluate the safety of VM202RY gene medicine injected into the cardiac muscle of incompletely revascularized area after CABG in patients with ischemic heart diseases.

Unique Protocol ID: VM202RY-VM01

Date of Protocol: Jan 1, 2007

CONFIDENTIAL

The information contained in this document is confidential and must not be disclosed to anyone outside the licensing authority, IRB/IEC, or anyone involved in the work, unless otherwise agreed in writing.

CONFIDENTIAL

Synopsis

Title	Open-label, non-comparative, dose-escalation, single-center, phase 1 trial to evaluate the safety of VM202RY gene medicine injected into the cardiac muscle of incompletely revascularized area after CABG in patients with ischemic heart diseases
Investigational product	Lyophilized plasmid DNA, pCK-HGFX7 (2mg/vial) containing 44mg sucrose and 36mg NaCl
Sponsor	ViroMed Co., Ltd.
Clinical site & Principal investigator	
 Clinical site: Seoul National University Hospital Principal investigator: [name]
Clinical protocol No.	VM202RY-VM01
Clinical design	Open-label, non-comparative, dose-escalating, single-center
Clinical phase	Phase I
Purpose of clinical trial	Safety evaluation of direct myocardial injection of VM202RY into coronary artery areas where complete revascularization by coronary artery bypass grafting is not achieved
Subject	All patients who are candidates for coronary artery bypass grafting are included, and patients in the surgical target area with decreased myocardial perfusion are expected to have incomplete revascularization in some myocardial areas due to poor vascular condition (e.g., calcified vessels, diffuse atherosclerotic vascular disease, small vessels with a diameter of less than 1 mm) that make it impossible to perform vascular anastomosis during surgery.

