8.2 Hypothesis

Direct myocardial injection of VM202RY during coronary artery bypass surgery in areas of incomplete reperfusion is a safe treatment method.

9. Investigational product

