13.2 Visiting schedule outline

13.2.1 Screening

Screening will be conducted for patients scheduled to undergo coronary artery bypass graft (CABG) surgery, starting from 21 days prior to surgery up to the day before surgery. During this period, written informed consent for participation in the clinical trial will be obtained, and all screening-related tests will be performed.

However, for coronary artery disease-related tests—such as MIBI SPECT, MRI, TTE, ECG, and Holter monitoring—previous results may be used if the tests were conducted within 21 days prior to gene administration. For coronary angiography (CAG), results may be used if the test was performed within 3 months prior to screening.

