13.4.2 Coronary artery bypass grafting (CABG)

1. Standardized Method: Under general anesthesia, pulmonary artery pressure is monitored using transesophageal echocardiography and a Swan-Ganz catheter. After median sternotomy, the left internal mammary artery and right gastroepiploic artery or right internal mammary artery are harvested using a skeletonization technique. Heparin (150 U/kg) is administered intravenously. A composite graft is created by connecting the right gastroepiploic artery or right internal mammary artery to the side of the left internal mammary artery. The left anterior descending artery is anastomosed using a local stabilizer on a beating heart, followed by anastomosis to the branches of the left circumflex artery and right coronary artery territory. After completing the anastomosis, protamine (0.15 mg/kg) is administered for neutralization, and the patency of the anastomosis is checked using a flowmeter before completing the surgery.
2. Distinguishing the Bypass Site from the Gene Injection Site: Although not strictly necessary for safety evaluation, for future efficacy assessments, the entire myocardial region will be segmented and evaluated by echocardiography, myocardial SPECT, and cardiac MRI. Therefore, it is expected to be possible to distinguish the bypass site from the gene injection site. This distinction will be particularly useful for efficacy evaluation in subsequent Phase 2 and Phase 3 studies involving control groups.
3. Target Group: All study subjects will undergo the procedure on Day 0, with VM202RY injected into the distal portion of the myocardium showing incomplete revascularization.
4. The goal is to confirm patency on angiography performed before discharge after surgery.

5. Surgery will primarily be performed on a beating heart. Patients requiring cardiopulmonary bypass due to hemodynamic instability will be excluded.

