14.2 Step 1: coronary artery bypass surgery and gene therapy period

During the gene therapy period (7 days), the subjects will be hospitalized for treatment.

1) Clinical evaluation

Symptoms of ischemic heart disease and physical examination: vital signs, auscultation findings, and other clinical examination findings. Canadian angina class, New York heart association functional classification

2) Laboratory test

(Note: The test results for anti-HGF antibodies and HGF protein in blood will be recorded in the case report form after the completion of the 24-week follow-up period.)

1. General Blood Tests

- Common Tests
 - Days 0, 1, 2, 5, and 7: CBC with differential count

- Days 1 and 7: ESR
- Additional tests by study group: None

2. General Chemistry Tests

- Days 1, 2, 5, and 7: Admission battery with electrolytes, lipid battery
- Days 1 and 7: CRP

3. Urinalysis: performed on Days 1, 5, and 7

4. ECG: follow-up on Days 0, 1, 2, 5, and 7

5. Cardiac Enzymes (CK/CK-MB, LDH, Troponin I): performed on Days 0, 1, 2, 5, and 7

6. Chest X-ray: performed on Days 0, 1, 2, 5, and 7

7. Echocardiography (TTE): performed on Day 7

8. Holter Monitoring: performed on Day 7

9. Blood Sampling for HGF Protein: performed on Day 7

(Tests on the day of surgery [Day 0] should be performed prior to the procedure.)

3) Intensive care and monitoring

1. Day of Surgery (POD#0 DAY): After surgery, the patient is transferred to the intensive care unit (ICU) with ventilatory support. The amount of bleeding is monitored through chest tubes inserted into the pericardium, mediastinum, and left and right pleural cavities in the operating room. Reoperation is considered in cases of significant bleeding (e.g., 500cc within 1 hour, 400cc/hr over 2 hours, or 300cc/hr over 3 hours). Continuous monitoring of systemic arterial pressure and pulmonary arterial pressure is performed. Medications (inotropics or vasodilators) and fluids are administered as needed based on hemodynamic status. Transient arrhythmias such as ventricular arrhythmias or atrial fibrillation are monitored via 24-hour ECG, and antiarrhythmic therapy (e.g., amiodarone) is administered if necessary. The patient's level of consciousness is assessed after awakening from anesthesia.

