17.4.3 Methods and criteria for efficacy evaluation

- 1) Changes in cardiac function

Changes in cardiac function can be evaluated using the left ventricular ejection fraction (LVEF) measured by cardiac MRI, myocardial SPECT, and echocardiography. Differences between treatment groups before and after VM202RY administration will be tested using the Kruskal-Wallis test.

Cardiac MRI methods and criteria

Analysis will follow the standard cardiac MRI protocols of the Department of Radiology at Seoul National University Hospital, using an appropriate segment model based on the patient's heart size. Parameters evaluated will include left ventricular volume (mL), wall motion index, myocardial thickness (mm), and LVEF (%). Comparisons will be made between baseline and follow-up measurements for each patient, as well as between treatment groups.

Myocardial SPECT methods and criteria

A 20-segment model, similar to the MRI analysis, will be used. Blood flow in each coronary artery distribution area will be assessed using a Bull's-eye view. Perfusion (%) will be evaluated from stress and rest images obtained using Dipyridamole. Additionally, the degree of systolic wall thickening (%), left ventricular volume, and function over time will be compared between groups. Left ventricular volume (mL), ejection fraction (%), and cardiac output (mL) obtained from SPECT will be used as supplementary data. Wall motion indices before and after surgery will be compared. Criteria for determining perfusion deficits and reversibility will follow established standard methods.

Echocardiography methods and criteria

From transthoracic echocardiography, left ventricular diameter (mm), ejection fraction (%), and wall thickness (mL) will be measured and compared with follow-up results after surgery. The Wall Motion Score Index will be calculated by dividing the myocardium into 16 segments and assigning a score to each area based on motion: [1 = normal, 2 = hypokinetic, 3 = akinetic, 4 = dyskinetic]. The total score for the entire myocardium and the right coronary artery region will be averaged by the number of segments.

- 2) Size of viable myocardium

Using cardiac MRI, the myocardial thickness at the gene injection site, the extent of late gadolinium enhancement, and local wall motion strength will be evaluated. Differences between groups before and after VM202RY administration will be tested using the Kruskal-Wallis test.

3) Improvement in Myocardial Ischemia

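### The objective promises verified effects and an optimal dosage, which an uncontrolled before-after design with concurrent CABG cannot deliver

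*Combined protocol and SAP*

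**What the plan says.** **Aim.** Under the preliminary-efficacy item, protocol 8.1 lists "Determination of the optimal dosage through dose escalation and verification of therapeutic effects". Section 13.1 describes the trial as a study of improved perfusion and contractility, with cohorts that serve to evaluate safety and therapeutic effect. Section 13.3 uses similar words about the review before each higher dose group. The only hypothesis, in 8.2, concerns safety: "Direct myocardial injection of VM202RY during coronary artery bypass surgery in areas of incomplete reperfusion is a safe treatment method". Section 11.4 says the trial is not meant to test statistical hypotheses, and 17.4 calls efficacy exploratory.

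**Design.** The synopsis gives it as "Open-label, non-comparative, dose-escalating, single-center". On treatment, 13.4.2 says: "All study subjects will undergo the procedure on Day 0, with VM202RY injected into the distal portion of the myocardium showing incomplete revascularization".

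**Timing of images.** Baseline is the screening scan before surgery. For SPECT, MRI and TTE, 13.2.1 says "previous results may be used if the tests were conducted within 21 days prior to gene administration". Follow-up SPECT, MRI and TTE are at Weeks 12 and 24 (14.3). One early post-operative image exists: "Echocardiography (TTE): performed on Day 7" (14.2).

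**Analysis.** In 17.4.3, "Comparisons will be made between baseline and follow-up measurements for each patient", and changes before and after VM202RY are tested between dose groups with the Kruskal-Wallis test. Viable myocardium (MRI) and ischaemia (SPECT) are scored in the injection region. Section 13.4.2 plans to segment the whole myocardium and says "it is expected to be possible to distinguish the bypass site from the gene injection site", but sees the main use of this in later controlled trials.

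**The concern.** Because CABG and injection fall on the same day, any change from before VM202RY to after it is also a change from before CABG to after it. Surgery is itself meant to improve perfusion and function. Without a control group, a before-after change cannot be attributed to VM202RY, whatever its size. The word verification claims such an attribution, and the words optimal dosage claim that efficacy can be ranked across doses.

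At stake is what the report may conclude on efficacy. The objective sets one standard, while 8.2, 11.4 and 17.4 set another. The plan also collects data that would describe the confounding (a post-operative TTE and segmental imaging), but 17.4.3 does not use either as a contrast.

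**Working it through.** **Step 1. The plan's own figure.** Three per group in three groups gives 3 × 3 = 9. With six per group after DLTs, 6 × 3 = 18. Both match the synopsis and 11.4. The documents give no alpha, power, effect size or SD for efficacy. Below I assume SD of change = 1, normal changes and a 5% level.

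**Step 2. Global scores (LVEF by three methods, LV volume, whole-heart wall motion).** Write the change in patient i at dose d as

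Y = C + D(d) + error,

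where C is the CABG effect and D(d) the drug effect. The expected mean change is C plus the average of D. Three different truths:

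| C | D at all doses | Mean change | Kruskal-Wallis rejection |
|---|---|---|---|
| 1 SD | 0 | 1.00 SD | 5.0% |
| 0 | 1 SD | 1.00 SD | 5.0% |
| 0.5 SD | 0.5 SD | 1.00 SD | 5.0% |

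The last column is exact. The test uses ranks only, so a constant added to every patient leaves it unchanged. Of the 1,680 ways to split nine ranks 3/3/3, 84 reach H ≥ 5.6, and 84/1,680 = 5.0%. Neither the mean change nor the test tells these cases apart.

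**Step 3. Injection-region MRI and SPECT.** Section 11.3 excludes a patient if anastomosis proves feasible at surgery, so the scored region is one whose vessel was not grafted. That takes most of the direct graft effect out of C. Four sources remain:

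- spill-over from nearby grafts;
- concomitant treatment (13.5 prohibits nothing and lists many drugs);
- time since surgery;
- for SPECT, regression to the mean, because inclusion criterion 2 selects on a stress-rest perfusion drop of at least 7% and screening SPECT is also the efficacy baseline.

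No comparator region is planned that would show how large these are. The documents give no repeatability for SPECT, so I put no figure on the last one.

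**Step 4. Comparison of doses.** C cancels if it is common to all cohorts, so a dose gradient is in principle separable. Simulated power with three per group (40,000 runs, C = 1 SD):

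| Drug effect at 0.5 / 1 / 2 mg (SD, assumed) | Exact critical value | Chi-square approximation |
|---|---|---|
| 0.25 / 0.5 / 1 | 9% | 2% |
| 0 / 0.5 / 1 | 12% | 3% |
| 0 / 1 / 2 | 33% | 12% |
| 0 / 1.5 / 3 | 64% | 33% |

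The plan does not say which reference distribution is used. The smallest attainable p is 6/1,680 = 0.0036 exact, or 0.027 by chi-square. An effect equal at all doses gives the 5% of Step 2. Cohorts are filled in order of consent (13.3), so a drift in case mix or surgery over time would also appear as a dose difference.

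**Step 5. The wording side by side.** Verification and optimal dosage (8.1) stand against a safety-only hypothesis (8.2), no hypothesis testing (11.4) and exploratory efficacy, done only where feasible (17.4).

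**The case against.** **The aim is labelled preliminary, and 17.4 says exploratory.** Both are true, and they make this a matter of wording rather than a failed confirmatory analysis. But a label does not change what the sentence beneath it promises. The passages contradict each other and should be reconciled.

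**The planned scores already separate drug from surgery.** This stands in part. Two of the three efficacy parameters are regional, and a common CABG effect cancels between doses. A reader might infer that no planned score can separate anything. The documents do not support that: it holds for the global scores only.

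**The plan does not act on efficacy.** This stands. A reader might infer that a rise in LVEF would be reported as verified and used to choose a Phase II dose. No passage says so. The tolerated-dose rule in 17.3.3 rests on DLTs alone, and although 11.4 and 13.3 speak of an appropriate dosage, they give no efficacy rule. Nor does 17.4.3 name a pooled within-patient test, so no false-positive rate of such a test belongs to this plan.

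**The added tables are not a clean control.** This stands too. Injected against grafted segments mixes a drug effect with the absence of a graft, and Day 7 offers TTE only, so it does nothing for perfusion. The tables can describe the confounding, not remove it.

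**Conclusion.** The concern holds as an over-worded objective together with an omitted descriptive contrast. It should be corrected, but it does not touch the primary safety analysis.

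- Global scores: confounding of VM202RY with CABG is complete in the before-after change. This needs no assumption beyond the schedule.
- Injection-region MRI and SPECT: confounding is reduced, by an amount the documents do not let one calculate. Change still cannot be attributed to VM202RY alone.
- Dose comparison: it does not turn a common CABG benefit into a false drug effect, but it cannot detect an effect equal across doses. Power is about 9% to 33% for the first three gradients, and 64% only for 0/1.5/3 SD. It cannot support an optimal dose.

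The power figures rest on assumed effects, normal changes with SD 1, a 5% level and 3/3/3 patients. Cohorts expanded to six after DLTs would do somewhat better, but would remain non-randomised.

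**What to change.** 1. Reword 8.1(b) and 13.1 as an exploratory description of changes after CABG plus VM202RY. State that change is not attributable to VM202RY alone and that no optimal dose is concluded from efficacy. Reconcile the similar words in 13.3 with this text.
2. In 17.4.3, for TTE, report the change from the Day 7 post-operative scan to Weeks 12 and 24 beside the change from screening.
3. In 17.4.3, report MRI and SPECT changes separately for injected, grafted and remaining segments.

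Items 2 and 3 stay descriptive, without tests.

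**Cost.** Wording and a few tables, with no added patient, visit or scan. The limits belong in the text: Day 7 function may be transiently affected by surgery, grafted segments carry the graft benefit, remaining segments may not be ischaemic, and segments of one heart are correlated.

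A concurrent CABG-only arm is not proposed. For an assumed effect of 1 SD (two-sided 5%, 80% power, normal approximation) it would need 2 × (1.960 + 0.842)² / 1² = 15.7, so 16 per arm. Nine against nine would have power of about 56%. That is a question for the later controlled trials that 13.4.2 foresees.

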8.2 Hypothesis

Direct myocardial injection of VM202RY during coronary artery bypass surgery in areas of incomplete reperfusion is a safe treatment method.

9. Investigational product

9.1 Composition, dosage, and formulation of the investigational product

Item	Investigational product
Content	pCK-HGFX7
Code	VM202RY
Formulation and appearance	White cake lyophilized and packaged in vials
Ingredients and contents	2mg/vial of lyophilized hepatocyte growth factor gene with 44mg sucrose and 36mg NaCl as DNA stabilizers
Dosage	
Preparation for administration: After CABG procedure, VM202RY (2mg/1 vial) is dissolved in 4mL of sterile distilled water, left at room temperature for 5 minutes to completely dissolve, and then placed in a 1mL sterile syringe (27G) and injected intramuscularly.Administration dose:
Cohort 1: intramuscular injection of 1 mL out of 4 mL VM202 RYCohort 2: intramuscular injection of 2 mL out of 4 mL VM202 RYCohort 3: intramuscular injection of 4 mL out of 4 mL VM202 RY
Storage	2 ~ 8°C

9.2 Packaging of investigational product

The VM202RY used in the clinical trial was manufactured by Strathmann Biotec (Germany). VM202RY (2 mg/1 vial) is labeled and provided to the clinical pharmacist.

9.3 Labeling of investigational product

The container or packaging label of the investigational drug used in the clinical trial shall include the following information as specified by KGCP:

- Subject number
- Indication that it is "For Clinical Trial Use"
- Product code name or the generic name of the active ingredient
- Lot number and expiration date or retest date
- Storage conditions
- Name of the manufacturer or importer of the drug
- Statement: "Not for use outside of the clinical trial"

9.4 Information on transport and storage of investigational product from the manufacturing site to the clinical trial site

9.4.1 Transport from the manufacturing site to the clinical trial site and quality inspection immediately after transport

VM202RY is delivered to the pharmacy of Seoul National University Hospital by air shipment, without X-ray screening at customs in Germany and South Korea, via biopharmaceutical import and delivery specialists (e.g., World Courier, TNT), and is maintained under refrigerated conditions (2°C–8°C) throughout transport by Strathmann Biotec AG.

Upon arrival at the pharmacy of Seoul National University Hospital, the clinical trial manager from ViroMed Co., [REDACTED] visually inspects the packaging condition, lyophilized state, and temperature conditions during transit. If no abnormalities are found, the VM202RY vials are stored in a refrigerator (2°C–8°C) at the pharmacy and used for the clinical trial.

The quality control (stability test) of the imported investigational product VM202RY is conducted in accordance with the stability testing criteria and methods submitted with the clinical trial application. Upon completion of the stability test, the results are reported to and filed with both the Korea Food and Drug Administration (KFDA) and the Clinical Trials Center Pharmacy at Seoul National University Hospital.

Since biologically active substances must be shipped only after coordination between the sender (sponsor), the carrier, and the recipient (investigator/site), the sender must follow the guidelines below to ensure safe and timely transportation:

- Comply with domestic and international shipping regulations.
- Ensure communication between the carrier and the recipient for smooth transport and receipt.
- Prepare the necessary shipping labels and declaration forms.
- Take steps to ensure prompt delivery.
- Send all relevant shipping documents to the receiving laboratory or facility.

9.4.2 Storage

VM202RY must be stored at a temperature of 2°C to 8°C, and refrigeration equipment capable of maintaining this set temperature must be used during storage. The refrigeration unit used to store VM202RY must be equipped with a locking mechanism, and temperature fluctuations and the condition of the refrigeration system must be carefully monitored and managed.

9.4.3 Retest date

The stability testing of the VM202RY investigational product (manufactured by Strathmann Biotec, Germany) will be conducted for 36 months from the start of the stability study, in accordance with the retest dates listed in the clinical trial application. The test result reports for each retest date will be kept on file at ViroMed Co., Ltd. and the Seoul National University Hospital Pharmacy.

Time point	Off storage date	Number of vials/storage temperature		Number of vials per time point
		-20°C	5°C	
0 months	16 March 2006	-	-	Release
1 month	16 April 2006	3	3	6
3 months	16 June 2006	3	3 + 11	17
6 months	16 September 2006	3	3	6
12 months	16 March 2007	3	3 + 11	17
18 months	16 September 2007	3	3	6
24 months	16 March 2008	3	3 + 11	17
36 months	16 March 2009	3	3	6

In addition, prior to the production of the clinical trial lot, a separate stability test was conducted according to the schedule below using the same formulation of the drug produced by TaKaRa Bio (Japan).

[figure not shown]
█████ stability testing beyond the planned 36-month stability testing period will be conducted in accordance with the stability testing standards and methods submitted in the clinical trial application, as follows:

If subject enrollment is completed before June 2009, stability testing will be performed on June 16, 2009.

If enrollment is completed before September, testing will be conducted on June 16 and September 16.

If enrollment is completed before December, testing will be conducted on June 16, September 16, and December 16.

These tests will be performed using the imported clinical trial VM202 final products stored at the Clinical Trials Center Pharmacy of Seoul National University Hospital. Upon completion of the stability tests, the results will be reported to and filed with the Korea Food and Drug Administration and the Clinical Trials Center at Seoul National University Hospital.

